8.4 Values of Potential Clinical Importance

8.4.1 Laboratory Parameters

A laboratory value that is outside the reference range is either high abnormal (value above the upper limit of the normal (ULN) reference range) or low abnormal (value below the lower limit of the normal (LLN) reference range). An abnormal laboratory value is not necessarily of potential clinical interest.

Table 3: Potential Clinically Important Values: Laboratory Panels

Test Name or Test combinations (Test code in lab data transfer)	Outlier Criteria (in conventional units delivered by lab)
Chemistry Panel	
Bilirubin, total (TBILIARC)	>1.5 x ULN
Alkaline phosphatase (ALPARCH)	>2.5 x ULN
SGOT, AST (ASTARCH)	>3 x ULN
SGPT, ALT (ALTARCH)	>3 x ULN
Drug Induced Liver Injury (DILI) Screening	AST or ALT >3 x ULN and Total Bilirubin >2 x ULN*
Urea nitrogen (BUNARCH)	>2.5 x ULN*
Creatinine, serum (CREATARCH)	>1.5 x baseline assessment* or change >0.3mg/dL since last visit
Glucose, blood (non-fasting) (GLURNARCH)	<55mg/dL or >160mg/dL*
Calcium (CAARCH)	<7mg/dL or >11.5mg/dL
Total protein, plasma or serum (TPARCH)	<5g/dL* or >9g/dL*

Test Name or Test combinations (Test code in lab data transfer)	Outlier Criteria (in conventional units delivered by lab)
Albumin (ALBARCH)	<3g/dL
Sodium (NAARCH)	<130mmol/L or >150mmol/L*
Potassium, serum/plasma (KARCH)	<3mmol/L or >5.5mmol/L
Uric acid, serum (UAARCH)	>10mg/dL Males* , >8mg/dL Females*
Gamma Glutamyl Transpeptidase (GGTARCH)	>2.5 x ULN
Phosphorus, inorganic (PHOSARCH)	<2.5mg/dL or >5mg/dL*
Lactate dehydrogenase (LDHARCH)	>3 x ULN*
Hematology and Differential Panel	
Hemoglobin (HGB)	<10g/dL
Platelet count (PLT)	<75 x 10 ⁹ /L or >500 x 10 ⁹ /L*
White Blood Cell Count (WBC)	<3 x 10 ⁹ /L or >16 x 10 ⁹ /L*
Neutrophils, absolute (ABSNEUT) Neutrophils, differential (NEUT)	<1.5 x 10 ⁹ /L <40%*
Lymphocytes, absolute (ABSLYMPH) Lymphocytes, differential (LYMPH)	<0.8 x 10 ⁹ /L <10% or > 50%
Urine Panel	
Protein (UPROTNARCH)	>20mg/dL

*flag level based on CSLB medical monitor recommendation; all other levels are established as based on CTCAE v5.0 moderate grade.

8.4.2 Vital Signs and Spirometry

To identify vital signs values of potential clinical importance, CSLB medical monitor recommendation will be used.

Table 4: Potential Clinically Important Values: Vital Signs and Spirometry

Test Name	Outlier Criteria
Vital Signs and Spirometry	
Systolic BP (mmHg)	
 • <100 or ≥ 140 • ≥ 140 AND increase >10 from reference visit
Diastolic BP (mmHg)	
 • <50 or ≥ 90 • ≥ 90 AND increase >10 from reference visit
Pulse (beats/ minute)	
 • <50 or ≥ 120 • ≥ 120 AND increase >15 from reference visit
Weight (kg)	
 • $\geq 10\%$ change (increase and decrease) from baseline assessment
Body Temperature ($^{\circ}\text{C}$)	
 • >39 or <35 (oral, tympanic, axilla or forehead)
CCI (%)	
 • Decrease >10 percentage points from reference visit

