End of Study (EOS)	The follow-up telephone call occurs 4 weeks after completing study treatment or early termination follow-up visit, whichever occurs later.
Reference visit	Reference visit for Treatment Period 1 is defined as the baseline of the study. Reference visit for Treatment Period 2 is defined as the most recent assessment before the first infusion in Treatment Period 2, after completion of planned treatment in Treatment Period 1.
Session	Each weekly dose of IgPro20 will be divided into two separate infusions and administered in two sessions: Session 1 and Session 2. Each treatment of IgPro10 will be administered over 2 to 5 consecutive days every 4 weeks.
Sequence	The study will consist of 2 sequences, Sequence A or Sequence B. Each subject will be randomized to 1 of the 2 treatment sequences.
Sequence A	IgPro20 0.5g/kg/week subcutaneous (SC) infusion in Treatment Period 1 + IgPro10 2g/kg/4 weeks intravenous (IV) infusion in Treatment Period 2
Sequence B	IgPro10 2g/kg/4 weeks IV infusion in Treatment Period 1 + IgPro20 0.5g/kg/week subcutaneous (SC) infusion in Treatment Period 2
Treatment	Treatment will be either IgPro20 0.5g/kg/week or IgPro10 2g/kg/4 weeks.

Treatment period	Each sequence will consist of two 16-week periods of treatment, a period of IgPro20 treatment and a period of IgPro10 treatment.
------------------	--

1 Introduction

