LLN	Lower limit of normal
CCI	CCI
MedDRA	Medical Dictionary for Regulatory Activities
CCI	CCI
PFT	Pulmonary function test
CCI	CCI
PID	Primary immunodeficiency
PK	Pharmacokinetics
SAE	Serious adverse event
SAF	Safety analysis set
SAP	Statistical analysis plan
SC	Subcutaneous
SD	Standard deviation
CCI	CCI
SMQ	Standardized MedDRA queries
SOC	System Organ Class
SSc	Systemic sclerosis
CCI	CCI
TEAE	Treatment-emergent adverse event
TEE	Thromboembolic event
CCI	CCI
ULN	Upper limit of normal
CCI	CCI

Glossary of Terms

Term	Definition
Baseline Value	The most recent assessment before the first infusion in Treatment Period 1.
End of Study (EOS)	The follow-up telephone call occurs 4 weeks after completing study treatment or early termination follow-up visit, whichever occurs later.
End of Treatment (EOT)	End of treatment is either end of Week 32 for completed subjects or at early termination visit.
Infusion	
IgPro10 An infusion comprises all IP exposure on one day of infusion. In the IgPro10 Treatment Periods, there are 2 to 5 consecutive days of infusions and so 2 to 5 Infusions planned per 4-week period.
 
IgPro20 An infusion comprises all IP exposure on one day (one session). In the IgPro20 Treatment Periods, there are 2 sessions and so 2 infusions planned per week.

Infusion Cycle (IgPro10 only)	One Infusion Cycle consists of 2, 3, 4 or 5 consecutive days of infusions with a planned total dose of 2 g/kg IgPro10 every 4 weeks. There are 4 planned Infusion Cycles of IgPro10 per IgPro10 Treatment Period in each Treatment Sequence.
Weekly Infusions (IgPro20 only)	A Weekly Infusion consists of 2 sessions (2 Infusions) with a planned total dose of 0.5 g/kg IgPro20 per week. There are 14 Weekly Infusions of IgPro20 per IgPro20 Treatment Period per each Treatment Sequence.
Infusion Session (IgPro20 only)	One Infusion Session consists of 1 infusion day. There are 2 Infusion Sessions within each weekly infusion with a planned total dose of 0.5 g/kg IgPro20 per week.
Protocol Deviation	
All instances when either subjects who have been entered in the study and / or the study sites deviate from the IEC / IRB-approved study protocol.
 
A key protocol deviation is any protocol deviation that could have a significant effect on the subject's safety, rights, or welfare and / or on the integrity of the study data.

Reference Visit	Reference visit for Treatment Period 1 is Week 1. Reference visit for Treatment Period 2 is Week 17.

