8.2.4 Baseline Definition

Baseline is defined as the most recent, non-missing value prior to the start date and time of the first study treatment infusion. Results from unscheduled visits will be taken into account.

If date is given for an assessment only and the time is missing, and the date of the assessment is the same as the date of the first study treatment infusion then this assessment is NOT considered baseline.

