8.4.3 ECG

Table 5: Potential Clinically Important Values: ECG

Test Name	Outlier Criteria
ECG	
ECG interpretation	Abnormal clinically significant (CS) at any study visit post baseline
Heart Rate (beats per minute)	$\leq 50^*$ or $\geq 100^*$
PR Interval (msec)	$\geq 200^*$
QRS Interval (msec)	$\geq 120^*$

Test Name	Outlier Criteria
QT, QTcB, QTcF (msec)	$\geq 480^*$ and $\leq 500^*$ $> 500^*$
QT, QTcB, QTcF, increase from baseline (msec)	$\geq 30^*$ and $< 60^*$ $\geq 60^*$

*flag level based on CSLB medical monitor recommendation; all other levels are established as based on CTCAE v5.0 moderate grade.

9 Study Population

Unless otherwise stated, all tables and listings in this section will be based on the Safety Analysis Set.

Individuals who do not meet the criteria for participation in this study (ie, screen failures) may be re-screened. In case of re-screening, the assessments from the re-screening visit will be summarized only, not the assessments from the original, failed screening attempt. Reasons for re-screening will be listed.

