For both **IgPro10** Treatment Periods and IgPro10 combined:

- Number of Infusion Cycles
- Planned and administered volume by Infusion Cycle and subject
- Administered total dose by Infusion Cycle and subject
- Duration of infusion by Infusion and Infusion Cycle
- Duration of treatment
- Maximum infusion rate by subject (mL/h, mL/kg/h, mg/kg/min)

There are several levels of aggregation for study drug exposure.

Level 1: Infusion. Observation in database extract.

Level 2: Infusion Cycle. One Infusion Cycle consists of 2-5 Infusions.

Level 3: Subject. All Infusion Cycles of the IgPro10 Treatment Period for a subject.

Table 8: Derivation of Exposure Variables IgPro10

Variable	Infusion	Infusion Cycle	Subject
Total planned volume (mL)	n/a	derived	sum
Total administered volume (mL)	entered	sum	sum
Initial infusion rate (mL/h)	entered	n/a	n/a
Initial infusion rate (mL/kg/h, mg/kg/min)	derived	n/a	n/a
Maximum infusion rate (mL/h, mL/kg/h, mg/kg/min)	derived	max	max
Actual total dose (g)	n/a	derived	derived
Duration of infusion	derived	sum	n/a
Duration of treatment	n/a	n/a	derived

derived= see derivation rule below

sum= sum of values of the lower level of the same variable

max= maximum of the values of the lower level of the same variable

Total Planned Volume (mL)

Level: Infusion Cycle

The total planned volume is entered once for each infusion. The value of the total planned volume will be taken from the entry of the first infusion of each Infusion Cycle.

Initial Infusion Rate (mL/kg/h)

Level: Infusion

$$\text{Initial Infusion Rate (mL/kg/h)} = \text{Initial Infusion Rate (mL/h)} / \text{reference weight (kg)}$$

Reference body weight is the baseline body weight. After a change of planned volume for the week, the most recent body weight before the change of planned volume is the reference weight.

Initial Infusion Rate (mg/kg/min)

Level: Infusion

$$\text{Initial Infusion Rate (mg/kg/min)} = 100 \text{ mg/mL} * \text{Initial Infusion Rate (mL/h)} / \text{reference body weight (kg)} / 60$$

Maximum Infusion Rate (all units)

Level: Infusion

The maximum infusion rate is the maximum of the initial infusion rate and all infusion rates after a change of infusion rate.

Actual Total Dose (g)

Level: Infusion Cycle, Subject

$$\text{Actual Total Dose (g)} = \text{Total Administered Volume (mL)} * 0.1 \text{ g/mL}$$

Duration of Infusion

Level: Infusion

$$\text{duration (min)} = \text{end time (min)} - \text{start time (min)}$$

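### Three outlier criteria (creatinine 1.5-fold, weight, QT/QTc increase) compare Period 2 values with the pre-study baseline, so by-product counts can repeat a Period 1 change or miss a Period 2 one

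*SAP*

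**What the plan says.** SAP 8.4.2 (Table 4) flags weight on a 10% or larger "change (increase and decrease) from baseline assessment". SAP 8.4.1 (Table 3) flags creatinine at ">1.5 x baseline assessment* or change >0.3mg/dL since last visit". SAP 8.4.3 (Table 5) has a row headed "QT, QTcB, QTcF, increase from baseline (msec", with bands of 30 to under 60 msec and 60 msec or more.

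The comparator is defined in SAP 8.2.4: "Baseline is defined as the most recent, non-missing value prior to the start date and time of the first study treatment infusion". The SAP Glossary agrees ("The most recent assessment before the first infusion in Treatment Period 1"). Nothing resets baseline for Period 2.

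The plan also has a period-specific comparator. The Protocol Glossary states: "Reference visit for Treatment Period 2 is defined as the most recent assessment before the first infusion in Treatment Period 2". The SAP Glossary names Week 17. In Table 4 the rise criteria for blood pressure and pulse use this reference visit, and so does the spirometry measure ("Decrease >10 percentage points from reference visit"). SAP Section 5, which lists departures from the protocol's analyses, gives no reason for the mix.

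On grouping, SAP 11.4 provides the laboratory outlier summaries by the Section 11 groups, which split by treatment and period. The outlier sentences for weight (SAP 11.5) and ECG (SAP 11.7) name no grouping. By-treatment display there is inferred from the sentence before each and from the general rule in SAP 7.2.

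**The concern.** SAP Table 1 starts every Period 2 assessment window at Week 17, and Protocol 3.3.1 plans no washout. A criterion anchored before Period 1 measures something wider than the window it is tabulated under. In Period 2 it measures the sum of the changes in both periods, while the table labels the count with the second product.

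Two errors can follow. A change that arose on the first product and persists could be counted under both products. A change that arises on the second product from a shifted Week 17 value could go uncounted. Safety of IgPro20 is the primary objective and safety of IgPro10 a secondary one, and acute renal injury is an adverse event of special interest. Readers of the by-product outlier tables will take the counts as what happened on that product.

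**Working it through.** No figure in the plan bears on this point, so the check sets the definitions side by side and then applies the written criteria.

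**1. Comparators as written**

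| Criterion | SAP table | Comparator |
|---|---|---|
| Blood pressure and pulse rise | 4 | reference visit |
| Spirometry fall | 4 | reference visit |
| Weight, 10% or more | 4 | study baseline |
| Creatinine, above 1.5-fold | 3 | study baseline |
| Creatinine, above 0.3 mg/dL | 3 | last visit |
| QT/QTc increase | 5 | study baseline |
| QT/QTc absolute limits (480, 500 msec) | 5 | none |

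**2. What a Period 2 flag measures**

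After Week 1, ECGs are scheduled only at Week 17 and end of treatment (EOT). For QT, then:

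Period 2 flag value = EOT − baseline = (Week 17 − baseline) + (EOT − Week 17).

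Only the second term arose in Period 2.

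**3. Worked values (baseline → Week 17 → later Period 2 value)**

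| Values | Against baseline | Against Week 17 |
|---|---|---|
| QTcF 410 → 442 → 442 msec | +32, flagged | 0, not flagged |
| QTcF 440 → 410 → 442 msec | +2, not flagged | +32, flagged |
| Weight 70 → 62.5 → 62.5 kg | 62.5/70 − 1 = −10.7%, flagged | 0%, not flagged |
| Weight 70 → 76 → 68 kg | 68/70 − 1 = −2.9%, not flagged | 68/76 − 1 = −10.5%, flagged |
| Creatinine 0.80 → 1.25 → 1.25 mg/dL | 1.25/0.80 = 1.56, flagged | 1.00, not flagged |
| Creatinine 1.20 → 0.75 → 1.15 mg/dL | 1.15/1.20 = 0.96, not flagged on this leg | 1.15/0.75 = 1.53, flagged |

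**4. The second creatinine leg**

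It is joined by OR, so it can add a flag but cannot remove one driven by baseline. It does repair part of the missed-change problem: in the last row a single step of 1.15 − 0.75 = 0.40 mg/dL would be caught. In Sequence B Period 2 the only scheduled creatinine values are Week 17 and EOT, so this leg in effect works from Week 17. In Sequence A Period 2, creatinine is also taken at Weeks 19, 23, 27 and 31. The same rise in two steps of 0.20 mg/dL would pass both legs.

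**5. Illustration of repeat flags, with zero true change in Period 2**

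The shifts and spreads below are assumptions; the documents give none. For QTc, P(flag against baseline) = 1 − Φ((30 − shift)/(SD × √2)). The Week 17 column sets the shift to 0. Creatinine is treated likewise on the log scale, and weight as a two-sided 10% limit.

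| Persistent Period 1 shift | Assumed spread per reading | Against baseline | Against Week 17 |
|---|---|---|---|
| QTc +20 msec | SD 8 to 12 msec | 19% to 28% | 0.4% to 4% |
| Creatinine 1.4-fold (1.5-fold leg only) | CV 8% to 12% | 27% to 34% | 0.02% to 0.8% |
| Weight −8% | SD 1% to 2% | 8% to 24% | under 0.1% |

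For QTc with SD 8: (30 − 20)/(8 × 1.414) = 0.88, which gives 19%; 30/(8 × 1.414) = 2.65, which gives 0.4%. With no Period 1 shift the two comparators give the same chance.

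**6. Weight of one subject**

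The target is 20 completers, 10 per sequence. One flag is 1/10 = 10 percentage points in a treatment-by-period cell and 1/20 = 5 points in a pooled treatment group.

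**The case against.** The case for leaving the tables alone has several parts.

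- **Endpoint wording.** Protocol 2.1.2 and 2.2.2 define these endpoints as changes from baseline, by treatment and period. That is correct, and baseline flags are valid as cumulative flags. But Protocol 10.3.2.2 specifies baseline or reference visit for laboratory values and vital signs, and Table 4 already uses the reference visit for three of its measures.
- **Week 17 is not drug-free.** The two products contain the same IgG substance at an equivalent four-week dose. If the second product sustains a shift, a Week 17 comparator hides it. Slow change can also be lost: QTcF 410 → 435 → 460 msec is +50 from baseline (flagged) but +25 from Week 17 (not flagged, and below 480). This stands, and it is why the baseline version must be kept alongside.
- **Covered elsewhere.** Laboratory changes and shifts are given against the reference visit, and weight and ECG changes against baseline/reference visit. No hypothesis is tested. This stands and limits the point to the outlier counts.
- **Balance.** With 1:1 randomization, each pooled treatment group holds one Period 1 arm and one Period 2 arm, so drift common to all subjects falls about equally on both products. This stands for common drift in the pooled tables. It does not help the by-period tables. Nor does it help a persistent effect of one product, which then also appears under the other.

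**Conclusion.** The point holds as an inconsistency with a limited effect. As written, three criteria use a comparator that does not match the treatment-and-period windows in which they are, or appear to be, reported. Persistent Period 1 changes could be repeated and some Period 2 changes missed. This rests on by-treatment display, which is explicit for laboratory values and inferred for weight and ECG. The number of subjects affected cannot be derived from the documents; the percentages in the working are conditional on assumed shifts.

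Stronger readings are not supported:

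- A reader might infer that the second product will show an excess of outliers by some multiple. That requires an assumed model of drift. For weight it also could not be a 32-week comparison, since the last scheduled weights are Week 31 (Sequence A) and Week 29 (Sequence B).
- A reader might infer that baseline is the wrong comparator, or that the second product caused none of a persisting change. The endpoint wording and the absence of a washout speak against both.
- A reader might infer that the protocol created the reference visit to judge each product from its own start. The glossary defines the term without giving that purpose.
- A reader might extend the point to the IgPro10 rates per kg in SAP 11.1 ("Reference body weight is the baseline body weight"). The next sentence there resets the weight after a change of planned volume, and the item is a descriptive exposure rate, not an outlier flag.

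**What to change.** For the creatinine 1.5-fold leg, the weight criterion and the QT/QTc increase, tabulate by-treatment and by-period outliers against the reference visit: study baseline for Period 1, Week 17 for Period 2. Keep the study-baseline version alongside, labelled as cumulative change over both products. State the grouping of the weight and ECG outlier tables in SAP 11.5 and 11.7.

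For Period 1, follow the Protocol Glossary, which equates the reference with study baseline. The SAP Glossary names Week 1, but creatinine is scheduled at Screening and not at Week 1.

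No flag limit changes, and Period 1 counts are unaffected. Chemistry, ECG and weight are already scheduled at Week 17 in both sequences, so no new data are needed. The cost is SAP wording, some programming and one more set of outlier rows.

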8.4.3 ECG

Table 5: Potential Clinically Important Values: ECG

Test Name	Outlier Criteria
ECG	
ECG interpretation	Abnormal clinically significant (CS) at any study visit post baseline
Heart Rate (beats per minute)	$\leq 50^*$ or $\geq 100^*$
PR Interval (msec)	$\geq 200^*$
QRS Interval (msec)	$\geq 120^*$

Test Name	Outlier Criteria
QT, QTcB, QTcF (msec)	$\geq 480^*$ and $\leq 500^*$ $> 500^*$
QT, QTcB, QTcF, increase from baseline (msec)	$\geq 30^*$ and $< 60^*$ $\geq 60^*$

*flag level based on CSLB medical monitor recommendation; all other levels are established as based on CTCAE v5.0 moderate grade.

9 Study Population

Unless otherwise stated, all tables and listings in this section will be based on the Safety Analysis Set.

Individuals who do not meet the criteria for participation in this study (ie, screen failures) may be re-screened. In case of re-screening, the assessments from the re-screening visit will be summarized only, not the assessments from the original, failed screening attempt. Reasons for re-screening will be listed.

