8.3 Study Periods Relative to Treatment

Definitions of the endpoint assessment and definition of start and end of study periods are presented in [Table 1](#) and [Table 2](#).

Table 1: Timing of Endpoint and Reference Assessments

	Definition	Start of Assessment Period	End of Assessment Period
By Treatment	1 IgPro20 Treatment Sequence A/ Treatment Period 1 and Treatment Sequence B/ Treatment Period 2	Week 1 Week 17	Week 17 ¹ Week 32
	2 IgPro10 Treatment Sequence A/ Treatment Period 2 and Treatment Sequence B/ Treatment Period 1	Week 17 Week 1	Week 32 Week 17 ²
By Treatment Sequence	1 Treatment Sequence A	Week 1	Week 32
	2 Treatment Sequence B	Week 1	Week 32
By Treatment and Treatment Period	1 IgPro20 in Treatment Period 1 Treatment Sequence A	Week 1	Week 17 ¹
	2 IgPro10 in Treatment Period 1 Treatment Sequence B	Week 1	Week 17 ²
	3 IgPro10 in Treatment Period 2 Treatment Sequence A	Week 17	Week 32
	4 IgPro20 in Treatment Period 2 Treatment Sequence B	Week 17	Week 32
Overall	1 Both Treatment Sequences, all Treatment Periods Treatment Sequence A/ Treatment Period 1, Treatment Sequence B/ Treatment Period 1, Treatment Sequence A/ Treatment Period 2, Treatment Sequence B/ Treatment Period 2	Week 1 Week 17	Week 17 Week 32

¹ Before first infusion of IgPro10.² Before first infusion of IgPro20.

Table 2: Treatment Periods

Treatment Sequence/ Treatment Period	Treatment	Start of Treatment Period	End of Treatment Period
Treatment Sequence A/ Treatment Period 1	IgPro20	Start date and time of the first IgPro20 Infusion	Start date and time of the first IgPro10 Infusion or EOS, if there is no IgPro10 Infusion
Treatment Sequence A/ Treatment Period 2	IgPro10	Start date and time of the first IgPro10 Infusion	EOS
Treatment Sequence B/ Treatment Period 1	IgPro10	Start date and time of the first IgPro10 Infusion	Start date and time of the first IgPro20 Infusion or EOS, if there is no IgPro20 Infusion
Treatment Sequence B/ Treatment Period 2	IgPro20	Start date and time of the first IgPro20 Infusion	EOS

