11.4 Clinical Laboratory Evaluations

The laboratory tests in Section 8.1.1 of the protocol will be summarized as described in this section.

Laboratory data will be presented in units provided by the central laboratory.

Lab values will be summarized descriptively by visit using only values from scheduled visits.

Separate summary tables for hematology, biochemistry, and virology laboratory tests will be produced. Changes from reference visit and shift tables are produced for hematology and biochemistry only. For a list of laboratory tests see Clinical Study Protocol, Table 1.

The denominator in percentage calculation at a scheduled visit will be based on the number of subjects with a non-missing value at that visit.

The following summaries will be provided by groups defined in [Section 11](#):

- All laboratory values by visit
- Laboratory value changes from reference visit
- Laboratory value shifts from reference visit with respect to the normal range
- Summaries of potential clinically important values will be provided according to the categories in [Section 8.4.1](#).

Listings to be produced are:

- All Laboratory values, including changes from Baseline and Reference visit, values outside normal range will be flagged

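### Most laboratory and ECG outlier criteria set no condition on the value before the product was started, so in this crossover a persistent abnormality can be counted under both products

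*SAP*

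**What the plan says.** SAP 8.4 lists the outlier criteria in Tables 3 (laboratory), 4 (vital signs and spirometry) and 5 (ECG). SAP 11.4 to 11.7 then build tables from them with one sentence, repeated in each section: "Summaries of potential clinically important values will be provided according to the categories in" the relevant part of 8.4. For laboratory data this is done by the product and period groups of SAP Section 11.

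Some criteria look back at an earlier value:

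- creatinine: ">1.5 x baseline assessment* or change >0.3mg/dL since last visit"
- a second line each for systolic and diastolic pressure: "AND increase >10 from reference visit", with a similar line for pulse
- weight, as a percentage change from baseline
- the redacted spirometry measure, as a fall from the reference visit
- "QT, QTcB, QTcF, increase from baseline (msec)"

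The rest are fixed levels or multiples of the upper limit of normal. The ECG-interpretation row reads "Abnormal clinically significant (CS) at any study visit post baseline".

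SAP 8.2.4 fixes one baseline for the whole study: "Baseline is defined as the most recent, non-missing value prior to the start date and time of the first study treatment infusion". The glossary makes Week 17 the reference visit for Treatment Period 2. Table 1 in SAP 8.3, titled "Timing of Endpoint and Reference Assessments", ends Period 1 at Week 17, with a footnote that this is before the other product is infused. It also starts Period 2 at Week 17, for example in the row "IgPro20 in Treatment Period 2 Treatment Sequence B".

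**The concern.** Each subject receives both products in turn, with no washout. A criterion that asks only whether a value is beyond a limit cannot tell an abnormality that arose on a product from one the subject brought to it. A long PR interval present at screening, or a low hemoglobin that developed in Period 1 and persisted, meets the criterion again at the second product's visits. The same holds for a change criterion anchored at study baseline: a rise that took place wholly in Period 1 still counts in Period 2.

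What is at stake is attribution. Changes in laboratory tests and ECG belong to the primary safety endpoint for IgPro20 and to the secondary safety endpoint for IgPro10. Outlier counts by product that contain the same persistent cases on both sides make the products look more alike, and can charge one product with what began on the other. The SAP avoids this for adverse events (SAP 8.3.1 assigns an event to a period by its onset) and partly for blood pressure and pulse.

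**Working it through.** The plan states no figure on this point, so there is none to reproduce. The check is a count of criteria, a trace of example subjects through the rules, and an illustration on assumed rates.

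**1. Count of criterion lines** (each bullet in Table 4 is one line; absolute and differential cell counts in Table 3 are separate lines)

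| SAP table | Lines | Refer to an earlier value | Level only |
|---|---|---|---|
| Table 3, laboratory | 25 | 1 (creatinine) | 24 (96%) |
| Table 4, vital signs and spirometry | 9 | 5 (second lines for systolic, diastolic and pulse; weight; spirometry) | 4 (44%) |
| Table 5, ECG | 6 | 1 (QT increase) | 5 (83%) |
| All | 40 | 7 | 33 (82.5%) |

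So the statement that most criteria are level-only is true of Tables 3 and 5 but not of Table 4. There, what has no companion change condition is the low limits for blood pressure and pulse, and temperature.

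**2. What the seven change criteria are anchored to**

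- Period reference visit: systolic, diastolic, pulse, spirometry.
- Study baseline: weight, QT increase, and the 1.5-fold part of creatinine. The other part of creatinine uses the last visit.

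**3. Example subjects traced through the rules**

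- PR at or above 200 ms at screening and throughout. It is met at Week 17 (after the first product) and at Week 32 (after the second), so it can be counted under both, though nothing changed.
- Sequence B, a clinically significant ECG first seen at the pre-infusion Week 17 visit and still present at Week 32. As an adverse event, its onset precedes the first IgPro20 infusion, so SAP 8.3.1 and Table 2 place it under IgPro10 only. As an outlier, Week 32 is post baseline, so it also counts under IgPro20.
- QTcF up 30 ms from baseline by Week 17 and flat afterwards. The change from the Week 17 reference is 0 ms, yet the QT-increase row is met at Week 32.

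None of these depends on how the Week 17 value itself is assigned.

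**4. Why Week 17 needs a rule.** In the protocol schedules, ECGs are done at Screening, Week 1 and Week 17 (the last two before infusion) and at Week 32. Two scheduled ECGs fall in the Table 1 window for Period 2, and one of them precedes the second product. The same is true of the scheduled hematology and chemistry panels for IgPro20 in Sequence B.

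**5. Illustration on assumed rates** (none are in the documents)

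Let q be the share of subjects with an outlier that is present before dosing and persists through both periods. With 20 subjects and no drug effect, the expected number flagged under each product is 20q, and the chance of at least one is 1 − (1 − q)^20.

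| q | Expected flags per product | Chance of at least one |
|---|---|---|
| 5% | 1 | 64% |
| 10% | 2 | 88% |
| 20% | 4 | 99% |

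If the true emergent rates e were 5% and 15%, an any-time count per product would show q + (1 − q)e:

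| q | Displayed rates | Ratio (true 3) | Difference (true 10 points) |
|---|---|---|---|
| 10% | 14.5% v 23.5% | 1.62 | 9 |
| 20% | 24% v 32% | 1.33 | 8 |
| 30% | 33.5% v 40.5% | 1.21 | 7 |

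The ratio shrinks a great deal and the absolute difference only a little. With a condition that the criterion was unmet before the product's first infusion, the persistent cases drop out of the counts in the first table.

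**The case against.** Much can be said for the plan.

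- **The change conditions are wider than blood pressure and pulse.** A reader might infer that the SAP deals with prior values only there. It also does so for creatinine, weight, spirometry and QT increase. This stands, and it narrows the point to the level-only lines and the three baseline-anchored criteria.
- **Week 17.** A reader might infer that the plan counts one Week 17 reading as an outlier for both products. The documents do not say so. Table 1's title and the glossary favour reading the start of a period as the reference and its end as the endpoint, and Table 2 starts each treatment period at first infusion. But the SAP applies Table 2 to adverse events and concomitant medication, and nothing in 8.4 or 11.4 to 11.7 excludes the reference value from outlier counts. Only that omission can be claimed.
- **Role of these tables.** A reader might take the outlier counts for the primary endpoint analysis. That endpoint is change from baseline, with its own summaries, so the outlier tables are supplementary.
- **Other routes.** Clinically significant ECG and laboratory findings are recorded as adverse events (protocol 8.1.1.5, 8.1.1.9 and 9.1.1) and assigned by onset. Hematology and biochemistry have shift tables from the reference visit. Both help interpretation, but neither alters the outlier counts. The shift tables use the normal range instead of these limits, and none is stated for ECG or vital signs.
- **Eligibility.** Exclusion criteria 8, 13, 17 and 19 remove some renal, cardiac, proteinuria and IgA abnormalities. Other ECG and laboratory abnormalities are left to the investigator's judgement (criteria 22 and 23). Pre-existing outliers are plausible, but their frequency is unknown.
- **Display.** Laboratory values are summarised by visit, and the table shells are separate documents, so a pooled any-time count is not certain. Separate visit rows would keep Week 17 apart. Aggregate rows would still not show whether the subject flagged at Week 32 was already flagged at Week 17.

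**Conclusion.** The concern holds for the supplementary outlier summaries. Followed as written, 33 of 40 criterion lines take no account of the value before the product was started, three of the seven change criteria carry a Period 1 change into Period 2, and the ECG-interpretation row does so explicitly. A persistent abnormality can therefore be counted under both products. This is more than missing detail, because the stated criteria themselves misattribute by product.

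The numerical effect cannot be derived from the documents. The rates in the illustration are assumptions, the second table also assumes an any-time count per product, and neither table is the trial's expected bias. The trial tests no hypothesis, and individual listings of about 20 subjects can be read by eye, which limits the harm. The correction is worth making because it is cheap and follows the rule the SAP already uses for adverse events.

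**What to change.** In SAP 8.4:

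1. Define a treatment-emergent outlier per period: the criterion is met at an assessment after the first infusion of that product and was not met at the last value before that infusion. For Period 1 this is the study baseline, and for Period 2 the pre-infusion Week 17 value. Use the last pre-infusion value instead of the Week 1 visit in Period 1, because hematology and chemistry are scheduled at Screening and not at Week 1. Say how a missing reference value is handled.
2. Count treatment-emergent outliers by product in 11.4 to 11.7, and show in a separate column the subjects who already met the criterion before first infusion.
3. State that the pre-infusion Week 17 value is the Period 1 endpoint and serves only as the reference for Period 2.
4. Use the period reference for the QT-increase, creatinine 1.5-fold and weight criteria in Period 2.
5. Reword the ECG-interpretation row to require clinical significance after the product's first infusion and its absence at that period's reference.

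The cost is SAP wording and one flag in the analysis datasets, with no new data. The drawback is small: a subject already beyond a limit who worsens further is not counted as new, and needs a listing or a separate worsening line.
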